6.1.1 Liver function tests

Change from the baseline in ALT, AST, alkaline phosphatase, total bilirubin, lymphocytes, and eosinophils will be summarized. Descriptive statistics, shift tables, and percentage of subjects with potentially clinically important values based on change from the baseline will be summarized for these tests as well. Box-Whisker plots will be provided. These summaries and plots will also be presented for the off-treatment period.

The number and percentage of subjects meeting the below liver enzymes criteria during the on-treatment period will be presented by treatment group:

- ALT >8x the upper limit of normal (ULN) or AST >8x ULN.
- ALT >5x ULN or AST >5x ULN.
- Total bilirubin >2x ULN and either ALT >3x ULN or AST >3x ULN.
- Prothrombin International Normalized Ratio (INR) >1.5 and either ALT >3x ULN or AST >3x ULN.

For the off-treatment period, number and percent of subjects with values within normal range at the off-treatment baseline and met the above criteria post baseline will be summarized.

The distribution of the time to first occurrence of an ALT or AST value >ULN while on study medication will be displayed with Kaplan-Meier curves. Subjects who complete or prematurely

discontinue the study medication without an ALT or AST value >ULN will be censored and the end of treatment date will serve as the time of censoring. The distribution of the time to first occurrence of an ALT or AST value >3x ULN will be summarized in the same way. The peak TB (total bilirubin) times the upper limit of the reference range (ULRR) will be plotted against the peak ALT times the upper limit of the reference range (ULRR), on a log10 scale (eDISH plot). These time-to-event plots and eDISH plot will be presented for the off-treatment period as well.

A listing of subjects with clinically important laboratory values will be provided that displays all values over time for subjects with at least one post-baseline clinically important laboratory value.

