**Attachment 3: Evaluation of Increased Liver Enzymes:**

The following process should be followed whenever assessments for a given subject indicate an elevation of alanine aminotransferase (ALT) or aspartate aminotransferase (AST)  $\geq 3\times$  upper limit of normal (ULN):

*1. Initial Investigation*

Within 24 to 72 hours of receipt of abnormal laboratory results, the investigator and study site are to perform the following:

- a. Repeat blood sampling:
  - Chemistry (include amylase if subject has abdominal pain or vomiting)
  - Complete hematology with eosinophil count
  - International normalized ratio (INR)
  - Hepatitis serology:
    - Hepatitis A: anti-HAV IgG, anti-HAV IgM
    - Hepatitis B: HBsAg, anti-HBc, anti-HBs
    - Hepatitis C: anti-HCV
    - Hepatitis E: anti-HEV IgG and IgM
    - Epstein Barr virus (EBV): anti-VCA IgG and IgM, anti-EBNA IgG
    - CMV: anti-CMV IgG and IgM.)
  - Anti-nuclear antibody (ANA)
  - One 5 mL sample of plasma for exploratory studies to evaluate the potential cause or risk factors for drug-related liver injury.
- b. Collect detailed history of present illness and additional medical history, to include:
  - Recent abdominal pain, pruritis, rash
  - Prior abnormal liver tests, liver disease, exposure to hepatotoxins, diabetes, obesity, marked hypertriglyceridemia, gallstone disease or family history of gallstone or liver disease
  - Record alcohol use, other meds including acetaminophen, NSAIDs and OTC herbal, vitamin, special diets, or nutritional supplements; any recent change in prescription drugs with start and stop dates; exposure to environmental chemical agents, or recreational drug use.
- c. Perform a full physical exam, with specific comments on:
  - Palpable liver, size, tenderness
  - Palpable spleen, size, tenderness
  - Jaundice
  - Stigmata of chronic liver disease: spider angiomata, gynecomastia, palmar erythema, testicular atrophy
- d. Schedule mandatory hepatic/pancreatic ultrasound

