2.3. Reference Start Date and Analysis Phases

The analysis reference start date (Study Day 1) is defined as the date of the first dose of study medication. The Study Day of an event start or stop date is defined relative to the analysis reference start date as:

- Event date – analysis reference start date + 1, if the visit/event date is on or after the analysis reference start date, or

- Event date – analysis reference start date -1, if the visit/event date is before the analysis reference start date

Study Days <1 will be considered in the Screening analysis phase; Study Days \geq 1 (there is no Study Day 0) will be considered in the Double-blind analysis phase.

For visit dates prior to, or on, the date of the last dose of study medication, an Analysis Day will be defined as above relative to the analysis reference start date. For visit dates after the treatment end date, an Analysis Day is defined relative to the treatment end date as: Visit date – treatment end date + 1.

- Analysis reference start date (date of first dose as above) for all timepoints after first dose (whether before or after last dose)
- For assessments after last dose, use last observation before last dose as the reference time point.

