2.4. Visit Windows

As subjects do not always adhere to the protocol visit schedule, the following rules are applied to assign actual visits to analysis visits. Listed below are the visit windows and the target days for each visit. The same definitions will apply to visits before or after the treatment end date using the Analysis Day as defined in Section 2.3 above. The time period description will be appended with '(On-Trt)' for post-baseline visits on or prior to the treatment end date. The time period description will be appended with '(Off-Trt)' for post-baseline visits after the treatment end date. If a subject has 2 or more actual visits in one visit window, the visit closest to the target day will be used as the protocol visit for that visit window. The other additional visit(s) will not be used in the summaries or analyses but they can be used for determination of clinically important endpoints. If 2 actual visits are equidistant from the target day within a visit window, the later visit will be used.

All assignments will be made in chronological order. Once a visit date is assigned to a visit window, it will no longer be used for a later time point except for the endpoint. Listed below (Table 1) are the visit windows and the target days for each visit defined in the protocol.

Table 1: Visit Windows for on and off-treatment Analysis

Scheduled Visit Number	Time period (label on output)	Time Interval (Day*)	Target Time Point (Day)
7	Baseline	-120 to 1	1
8	Week 2	2 to 22	15
9	Week 4	23 to 36	29
10	Week 6	37 to 50	43
11	Week 8	51 to 64	57
12	Week 10	65 to 81	71
13	Month 3	82 to 106	92
14	Month 4	107 to 134	120
15	Month 5	135 to 165	148
16	Month 6	166 to 211	183
17	Month 8	212 to 256	239
18	Month 9	257 to 288	274
19	Month 10	289 to 333	302
20	Month 12	334 to 410	365
21	Month 15	411 to 501	456
22	Month 18	502 to 592	547
23	Month 21	593 to 683	638
24	Month 24	684 to 774	729
25	Month 27	775 to 865	820
26	Month 30	866 to 956	911
27	Month 33	957 to 1047	1002
28	Month 36	1048 to 1138	1093
29	Month 39	1139 to 1229	1184
30	Month 42	1230 to 1320	1275
31	Month 45	1321 to 1411	1366
32	Month 48	1412 to 1502	1457
33	Month 51	1503 to 1593	1548
34	Month 54	1594 to 1684	1639
	Month >54	1685 to ∞	1685

* Relative to analysis reference start date if visit date is prior to or on the treatment end date. Relative to treatment end date if visit date is after treatment end date.

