‘End point (On-Trt)’ is defined as the last available post-baseline result among the on-treatment visits. Unscheduled visit results are included in this definition and will be considered as the endpoint value if the unscheduled visit result is the last post-baseline result available among all on-treatment visits. ‘Baseline (Off-Trt)’ will be defined as the same as ‘End point (On-Trt)’. ‘End point (Off-Trt)’ is defined similarly to ‘End point (On-Trt)’ but based on off-treatment visits.

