6.1 Adverse Events

The verbatim terms used in the CRF by investigators to identify adverse events will be coded using the Medical Dictionary for Regulatory Activities (MedDRA). Any AE occurring on or after the date of the initial administration of study medication through the day of last dose plus 7 days is considered to be treatment emergent. If the event date is recorded as partial or completely missing, then the event will be considered to be treatment emergent unless it is known to be prior to the first administration of study medication based on a partial onset date or resolution date. All reported treatment-emergent adverse events will be included in the analysis. For each adverse event, the number and percentage of subjects who experience at least 1 occurrence of the given event will be summarized by treatment group. AEs in the off-treatment period are the AEs with onset more than 7 days after the last dosing.

Summary tables will be provided for:

- AEs
- AEs with a fatal outcome

- Serious AEs (SAEs)
- AEs leading to discontinuation of study medication (events with action taken of ‘drug withdrawn’)
- AEs leading to termination of study participation (events associated with a trial termination reason of ‘adverse event’)
- AEs by severity

AEs will also be summarized by age group, by gender, and by race. In addition to the summary tables, listings will be provided for subjects who:

- Died
- Had SAEs
- Had AEs leading to discontinuation of study medication or termination of study participation

The above listings will include events with onset during the screening phase.

Incidence of other treatment-emergent adverse events of special interest will be summarized. Hypopigmentation related and retinal related adverse events are identified by the investigator on the AE eCRF page and include:

- Hypopigmentation Related Adverse Events
 - Hair and skin hypopigmentation (events related to lighting hair, skin coloration, or iris coloration)
- Retinal Related Adverse Events
 - Retinal changes

Hepatic related treatment-emergent adverse events will also be summarized. Adverse events related to abnormal LFTs are defined as follows:

Events belonging to the MedDRA Drug Related Hepatic disorders SMQ – comprehensive search

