Attachment 6: Potentially Clinically Important Criteria for Laboratory Tests

Test	Criteria for Low PCI Values	Criteria for High PCI Values
Hematology		
WBC Leukocytes (x10E9/L)	<3	>16
Eosinophils (x10E9/L)	NA	> 0.6
Lymphocytes (x10E9/L)	<0.8	NA
Monocytes (x10E9/L)	NA	> 1.0
Neutrophils, Segmented (x10E9/L)	<1.5	> 8.0
Platelets (x10E9/L)	< 75	> 700
Hematocrit (fraction)	<0.3	> 0.5 females, > 0.55 males
Hemoglobin (g/L)	value <100 or change from baseline <= - 20	>165 females, >185 males
MCV (fL)	< 75	>105
Chemistry		
Serum Albumin (g/L)	< 30	NA
Alkaline Phosphatase (U/L)	NA	> 3 ULN
ALT (U/L)	NA	> 3 ULN
AST (U/L)	NA	> 3 ULN
Bicarbonate (mmol/L)	< 17	> 32
Bilirubin (umol/L)	NA	> 3 ULN
BUN (mmol/L)	NA	> 1.5 ULN
Calcium (mmol/L)	< 2.0	> 2.7
Chloride (mmol/L)	< 94	> 112
Creatine Kinase (U/L)	NA	> 1.5 ULN
Creatinine (umol/L)	NA	> 1.5 ULN
GGT (U/L)	NA	> 3 ULN
Glucose (mmol/L)	< 3.9	> 5.6
Phosphate (mmol/L)	< 0.7	> 1.7
Potassium (mmol/L)	< 3	> 5.5
Protein (g/L)	< 60	> 80
Sodium (mmol/L)	< 135	> 145
Urate (umol/L)	< 150	> 500
Urinalysis		
pH	< 4	> 8
Specific Gravity	NA	> 1.035

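### SAP 6.1.1: a raised INR, or newly raised bilirubin, from a liver work-up drawn after a permanent stop is not counted on-treatment, and is also lost off-treatment if the normal-range filter applies to ALT/AST

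*SAP*

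**What the plan says.** **The criterion.** SAP 6.1.1 (Liver function tests) lists four liver criteria to be counted by arm for the on-treatment period. Two are combined criteria: total bilirubin >2xULN with ALT or AST >3xULN, and "Prothrombin International Normalized Ratio (INR) >1.5 and either ALT >3x ULN or AST >3x ULN". For the off-treatment period it counts the "number and percent of subjects with values within normal range at the off-treatment baseline and met the above criteria post baseline". It does not say which analytes must be normal.

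**The period rule.** SAP 2.4 labels results off-treatment "for post-baseline visits after the treatment end date"; results on or before that date are on-treatment. SAP 2.3 adds: "For visit dates after the treatment end date, an Analysis Day is defined relative to the treatment end date". No lag is given for laboratory values. For adverse events, SAP 6.1 does give one: onset "through the day of last dose plus 7 days is considered to be treatment emergent".

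**The off-treatment baseline.** SAP 2.4 sets it equal to the on-treatment end point, which "is defined as the last available post-baseline result among the on-treatment visits", unscheduled results included. SAP 2.3 also has a bullet that takes the last observation before last dose as the reference for later assessments, without limiting it to post-baseline results.

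**Where INR comes from.** Protocol 9.9.6 schedules coagulation tests at screening only. Protocol Attachment 3 adds INR to the work-up for ALT or AST at or above 3xULN: "Within 24 to 72 hours of receipt of abnormal laboratory results, the investigator and study site are to perform the following". The later follow-up draws in that attachment are serum chemistry.

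**When drug stops.** Protocol 10.2 and Attachment 3 require discontinuation for ALT or AST >5xULN in the first 3 months, or >8xULN later, without needing an INR. Protocol 10.2 also says values above 3xULN should be confirmed within 24 to 72 hours.

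**The concern.** The INR row depends on a test drawn after the enzyme result has been acted on. If the action is to stop drug for good, the INR falls just past a cut-off that has no lag, and the off-treatment filter can then remove the subject because of the enzyme elevation that prompted the test. An error of this kind can only lower the on-treatment count, and it concerns subjects whose drug was stopped promptly.

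Hepatic safety is why dosing ended, and descriptive safety summaries are a main remaining output of the amended SAP. SAP Attachment 6, "Potentially Clinically Important Criteria for Laboratory Tests", has rows for ALT and AST but none for INR, so the 6.1.1 row is the only planned laboratory count of INR by arm. As planned, a zero in that row could mean that no one met the criterion or that the INR was drawn a day or two after the last dose.

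**Working it through.** The plan gives no figure to reproduce; the check applies its rules to dated cases.

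**Worked case.** Let day 0 be both the day the abnormal result is received and the day of last dose.
- Work-up at 24 to 72 hours: day +1 to +3.
- Off-treatment Analysis Day (SAP 2.3) = visit date − treatment end date + 1 = 2 to 4. This lies in the off-treatment Week 2 window, days 2 to 22 (SAP 2.4, Table 1).
- On-treatment row: the cut-off is day 0, so the INR is not counted.
- Off-treatment row with the filter on ALT/AST: the baseline is the triggering value, above 5x or 8xULN, so the subject is excluded.
- With a last-dose-plus-7-days limit: +3 ≤ +7, so the INR is counted on-treatment. If the last dose was the day before receipt, the draw is on day +2 to +4, still within +7.

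**Order of events.** Each case below has ALT above 3xULN in the triggering and work-up samples and INR above 1.5 in the work-up. SAP 2.4 alone defines the off-treatment baseline.

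| Sequence | On-treatment | Off: ALT/AST and INR normal | Off: ALT/AST normal | Off: INR normal |
|---|---|---|---|---|
| A. Last dose after trigger, before draw | no | no | no | no |
| B. Last dose on day of draw | yes | no | no | no |
| C. Drug stopped after draw | yes | no | no | no |
| D. Drug stopped before triggering sample, last on-treatment ALT normal | no | no | yes | no |
| E. As A, with an earlier normal on-treatment INR | no | no | no | yes |

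**Effect of the SAP 2.3 bullet.** If a normal screening INR may serve as the reference, the last column of A becomes yes. The other two off-treatment columns of A stay no, because ALT/AST is raised whichever reference is used.

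**Bilirubin.** Total bilirubin is in the routine chemistry panel (Protocol 9.9.6), so the triggering sample already carries one value. If that value exceeds 2xULN with ALT/AST >3xULN, the subject is counted on-treatment. If bilirubin first exceeds 2xULN in a work-up drawn after the last dose, it is off-treatment and the filter on ALT/AST excludes the subject in the same way.

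**Size per subject.** SAP 1 gives 557 randomized. Assuming equal arms, 557/3 = 185.7, about 186. One missed subject changes that arm's percentage by 1/186 = 0.54 points.

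**The case against.** **A reader might infer that the subject is lost from both periods however the filter is read.** The documents do not support that. The SAP 2.3 bullet is not confined to post-baseline results and prothrombin time is measured at screening. With the filter on INR alone, a normal screening INR, or a normal INR from an earlier work-up, would let the subject count off-treatment. This stands, and it limits the point to the readings in which ALT/AST must be normal. Even on the INR-only reading the event is credited to the off-treatment period.

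**A reader might also infer that the row undercounts stops made because of INR.** Where INR >1.5 is itself the reason for stopping, it must be known first. Unless dosing was already paused, it was then drawn on treatment and is counted. The subjects at risk mainly stopped on another criterion, such as >5xULN or >8xULN, and appear in that row.

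**The sequence is uncertain.** Repeat chemistry and INR belong to the same work-up. If the stop waits for the confirmatory ALT/AST, the INR is on-treatment; a hold followed by resumption also keeps it on-treatment. The documents do not say which result triggers the stop. A stop on the first result is allowed, however, and there is a second route: all dosing stopped on 17 May 2018, so a triggering sample just before that date with a work-up just after it gives sequence A.

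**The cases are visible elsewhere.** Subjects meeting a discontinuation criterion are to be reported as SAEs (Protocol 10.2, 12.3.4), and SAP 6.1 tabulates and lists SAEs. ALT/AST >3xULN places a subject in the laboratory listing with all values over time. No formal hypothesis testing is planned. These facts hold the point to a minor one; they do not correct the row.

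**Conclusion.** The gap follows from the written rules in one situation: an on-treatment ALT/AST elevation, a permanent stop before the work-up draw, and INR >1.5 (or bilirubin first above 2xULN) in that draw with ALT/AST still >3xULN. The result is then not counted on-treatment. It is not counted off-treatment either when the normal-range condition covers ALT/AST.

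Two of the four criteria in SAP 6.1.1 are touched, INR more than bilirubin because bilirubin is already measured in the triggering sample. The number of subjects cannot be estimated, since the documents give neither the frequency of stops before the draw nor that of INR >1.5; it may be zero. Each missed subject is worth about 0.5 percentage points in an arm of about 186, assuming equal arms.

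The documents also do not establish which arms would lose subjects. Protocol 1.4 reports 11 enzyme elevations >3xULN in studies longer than 1 month (9 on active drug, 1 on placebo, 1 blinded), but it gives no arm denominators and concerns enzymes, not INR. Severity is minor.

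**What to change.** Add to SAP 6.1.1:

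*For the combined INR and total bilirubin criteria, values from the protocol Attachment 3 work-up drawn no later than last dose plus 7 days are assigned to the on-treatment elevation that triggered it.*

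Beside the INR row, show by arm the number of subjects with on-treatment ALT or AST >3xULN and how many of them had an INR in that episode. A zero can then be read against how many were tested.

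Seven days is the window SAP 6.1 already uses for adverse events, and it covers the worked case. Covering both combined rows avoids two cut-offs among the combined criteria. For draws inside the window, the question of which analytes the off-treatment filter covers no longer decides whether the subject is counted.

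The cost is one sentence and two table rows, with no new data and no protocol change. The downside is that a few changes that began after the stop may be credited to treatment.

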### **12.3.4. Adverse Drug Reactions**

Elevated liver enzymes have been identified as an adverse drug reaction (ADR) (see Investigator Brochure). The procedures for reporting these ADRs are described in detail in Attachment 3.

Subjects who meet the criteria for discontinuation of study treatment should have the event reported as an SAE and should follow the SAE reporting process (Section 12.3.2).

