## 2. Follow-up Blood Sampling and Ongoing Contact with Medical Monitor

After the initial investigation, regardless of results, serum chemistry is to be performed (using the central lab retest kit) per the schedule below (Table 3) and close contact with the medical monitor with a minimal contact frequency (as outlined in the table) is also expected.

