## 4. Discontinuation of Study Treatment:

For subjects during the first 3 months of treatment with study drug, treatment must be discontinued if any of the following occurs:

- ALT or AST  $> 5 \times \text{ULN}$
- ALT or AST  $> 3 \times \text{ULN}$  and total bilirubin  $> 2 \times \text{ULN}$  or INR  $> 1.5$
- ALT or AST  $> 3 \times \text{ULN}$  with the appearance of fatigue, nausea, vomiting, right upper quadrant pain or tenderness, fever, rash, and/or eosinophilia  $> 5\%$

For subjects that have completed 3 months of treatment with study drug, treatment must be discontinued if any of the following occurs:

- ALT or AST  $> 8 \times \text{ULN}$

- ALT or AST  $> 5 \times \text{ULN}$  for more than 2 weeks
- ALT or AST  $> 3 \times \text{ULN}$  and total bilirubin  $> 2 \times \text{ULN}$  or INR  $> 1.5$
- ALT or AST  $> 3 \times \text{ULN}$  with the appearance of fatigue, nausea, vomiting, right upper quadrant pain or tenderness, fever, rash, and/or eosinophilia  $> 5\%$

5. SAE Reporting

Subjects who meet the criteria for discontinuation of study treatment should have the event reported as an SAE and should follow the SAE reporting process, as outlined in Section 12.3.2 of the protocol.

6. Continuation or Resumption of Study Treatment:

Study treatment may continue in asymptomatic subjects who do not meet the discontinuation rules, however, the investigator/site must adhere to the blood sampling and contact with Medical Monitor schedule in Table 3.

For subjects resuming treatment after an interruption of less than 7 days, the blood sampling schedule in Table 3 should be followed. In case treatment is resumed after interruption of more than 7 days, resumption of treatment must be discussed with and approved by the sponsor medical monitor. In these cases, follow-up blood sampling should occur weekly for the first month and thereafter Table 3 should be followed. Dosages should be at the same level as before the interruption.

7. Characterization of T-cell Response in Subjects Previously Treated with atabecestat

Additional blood draws of 120 mL may be taken from subjects with elevated hepatic enzymes for PBMCs to be isolated and used in an optional immunologic sub study (see Attachment 4).

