1. INTRODUCTION

This statistical analysis plan (SAP) contains definitions of analysis populations, derived variables and statistical methods for the analysis of efficacy and safety for study 54861911ALZ2003.

Screening, randomization, and dosing in this study was stopped on 17 May 2018. Randomized subjects were to continue in the double-blind treatment phase without treatment (as allowed by protocol) for approximately 3 to 6 months from cessation of dosing. This permitted continued safety monitoring of the subjects per protocol. The planned last-patient-out date is 17 September 2018, except for some subjects who may require further follow-up.

At the time of cessation of screening and randomization, 557 (34%) subjects of the planned 1650 had been randomized. The planned duration of treatment was 54 months. As of the time of cessation of dosing, no subject had more than 27 months of treatment and 447 had 12 months of treatment or less.

As a result of the significantly reduced sample size, the objectives of the study as stated in the protocol and in Section 1.1 below cannot be evaluated. Safety outcomes will be summarized with descriptive statistics. The planned interim analysis of CSF A β ₁₋₄₀ was performed but other planned interim analyses will not be performed. Between-group comparisons of selected efficacy outcomes will be performed. Other efficacy outcomes will be summarized with descriptive statistics

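### SAP 6.1.1 omits from both of its by-arm counts any subject who first meets a graded liver criterion after the last dose from an abnormal last on-treatment value

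*SAP*

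**What the plan says.** SAP 6.1.1 (Liver function tests) plans two tabulations of the four criteria. The first reads: "The number and percentage of subjects meeting the below liver enzymes criteria during the on-treatment period will be presented by treatment group". The second, for the off-treatment period, reads: "number and percent of subjects with values within normal range at the off-treatment baseline and met the above criteria post baseline will be summarized".

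SAP 2.4 (Visit Windows) fixes the boundary. The on-treatment label is used "for post-baseline visits on or prior to the treatment end date", and everything later is off-treatment. It also fixes the reference value: "Baseline (Off-Trt)’ will be defined as the same as ‘End point (On-Trt". That endpoint is the last available on-treatment result, unscheduled results included.

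Other liver outputs are planned for the off-treatment period:

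- counts of potentially clinically important values (ALT, AST and bilirubin each above 3x ULN; SAP 6.1 Clinical Laboratory Tests and Attachment 6);
- shift tables;
- time-to-event plots for ALT or AST above ULN and above 3x ULN;
- an eDISH plot for each period.

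A listing shows all values for subjects with a clinically important result.

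**The concern.** The two counts do not cover all cases. The on-treatment count ends at the last dose, and the off-treatment count admits only subjects who were normal at that point. A subject who leaves treatment with raised enzymes and then worsens into a higher grade is missed by both.

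This is the group of most interest. The amendment 6 rationale in the protocol gives frequent hepatic enzyme elevations as the reason dosing stopped. Protocol 12.3.4 states: "Elevated liver enzymes have been identified as an adverse drug reaction (ADR"). Liver-triggered stops, and so the omissions, are plausibly more common in the active arms. The SAP introduction says the study objectives can no longer be evaluated and that safety will be described, so the liver severity tables are among the main remaining outputs.

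The off-treatment period is also long enough to matter: "Randomized subjects were to continue in the double-blind treatment phase without treatment (as allowed by protocol) for approximately 3 to 6 months from cessation". For subjects worked up for ALT or AST at or above 3x ULN, Protocol Attachment 3 adds: "After the initial investigation, regardless of results, serum chemistry is to be performed (using the central lab retest kit) per the schedule below".

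**Working it through.** **1. The rule applied to one subject.** The last on-treatment ALT is 6x ULN and the off-treatment peak is 9x ULN. The subject is in the on-treatment above-5x count. The on-treatment above-8x count misses the subject because 9x came after the last dose. The off-treatment above-8x count misses the subject because 6x is not within normal range. The 8x crossing is counted nowhere.

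**2. Check by enumeration.** The grid values are assumptions, used only to test the logic: ALT at 0.8, 2, 4, 6 or 10x ULN; bilirubin at 0.7, 1.5 or 2.5x ULN; INR at 1.0 or 1.8. That gives 5 × 3 × 2 = 30 states. Crossing the last on-treatment state (taken as the on-treatment peak) with the off-treatment peak gives 30 × 30 = 900 profiles. One state is normal on all three tests. If k states meet a criterion:

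- met at some time: 900 − (30 − k)²
- in the on-treatment count: 30k
- added by the off-treatment count: k × 1
- in neither count: the first line minus the other two

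| Criterion | k | Met at some time | On-treatment | Off-treatment | Neither |
|---|---|---|---|---|---|
| ALT >8x | 6 | 324 | 180 | 6 | 138 |
| ALT >5x | 12 | 576 | 360 | 12 | 204 |
| Bilirubin >2x with ALT >3x | 6 | 324 | 180 | 6 | 138 |
| INR >1.5 with ALT >3x | 9 | 459 | 270 | 9 | 180 |

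These are grid profiles, not rates in subjects. Every omitted profile has an abnormal off-treatment baseline, so the baseline restriction is the only cause; without it, the last column is 0. Every omitted profile also has off-treatment ALT above 3x ULN, so it stays visible in the above-3x count but not under its grade.

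**3. The stopping rules against the four criteria** (Protocol 10.2 and Attachment 3). The early rules begin: "For subjects during the first 3 months of treatment with study drug, treatment must be discontinued if any of the following occurs". The combined bilirubin or INR rule is read here as needing ALT or AST above 3x ULN in both branches.

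| Period | Trigger | SAP criteria not implied by the trigger |
|---|---|---|
| First 3 months | >5x | >8x, bilirubin, INR (3) |
| First 3 months | >3x with bilirubin or INR | >5x, >8x, the other of the two (up to 3) |
| First 3 months | >3x with symptoms | all 4 |
| After 3 months | >8x | bilirubin, INR (2) |
| After 3 months | >5x for over 2 weeks | >8x, bilirubin, INR (3) |
| After 3 months | >3x with bilirubin or INR | up to 3 |
| After 3 months | >3x with symptoms | all 4 |

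In 7 of 7 routes ALT or AST is above 3x ULN at the trigger. If that sample is the last on-treatment value, the subject is barred from all four off-treatment counts while 2 to 4 criteria could still be met for the first time.

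**4. Scale per subject.** SAP 1 gives 557 randomized. Assuming 1:1:1 held, 557/3 = 185.7 per arm. One missed subject is 1/185.7 = 0.54 points; five would be 5/185.7 = 2.7 points. The range of 1 to 5 is an assumption.

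**The case against.** **Values may fall after stopping.** Protocol 1.4 reports that in the earlier study enzymes moved back towards normal once the drug was discontinued, and the gap needs the opposite. The same section gives 11 subjects above 3x ULN among more than 200, at most 11/200 = 5.5%, or about 10 in an arm of 186. Five missed would mean about half of them first reaching a new grade after stopping. This stands as a reason to expect small numbers. It does not make the number zero, and amendment 6 later calls the elevations frequent.

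**These subjects are captured elsewhere.** Meeting a liver stopping rule is reported as an SAE, and SAP 6.1 (Adverse Events) tabulates SAEs, discontinuations and hepatic events by arm. The off-treatment eDISH plot shows bilirubin against ALT. This also stands, but none of these outputs gives a by-arm count at 5x, at 8x or for INR. The eDISH plot omits AST and INR. Because it is drawn per period, an ALT peak before the last dose and a bilirubin peak after it are not plotted together.

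**SAP section 6 opens by promising all safety summaries for both periods.** That general sentence does not override the specific restriction in 6.1.1.

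**INR is rarely sampled.** Coagulation is a screening-only test, and INR otherwise appears in the Attachment 3 work-up 24 to 72 hours after an abnormal result is received, so there are few chances for a late INR crossing. But if dosing stops on the triggering result, that work-up INR is itself off-treatment with an abnormal ALT or AST baseline and falls in neither count.

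**A normal-baseline count is a legitimate new-onset measure.** It is, and the SAP uses baseline-restricted denominators for the C-SSRS too. The weakness is that it is the only off-treatment count of these criteria.

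**Conclusion.** The concern holds. As written, SAP 6.1.1 has neither an any-time count nor an unrestricted off-treatment count of its four liver criteria. A first crossing after the last dose from an abnormal ALT or AST is tabulated nowhere for that criterion. As measures of how many subjects ever met each criterion, the two counts can only be too low, plausibly more so in the active arms.

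The number of subjects affected cannot be determined from the documents; the scale is about 0.5 percentage points per missed subject per arm. The threshold that triggered a stop is normally already counted on-treatment, so the gap concerns criteria first met later.

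The SAP does not say which tests must be within normal range. If only the tests in the given criterion must be normal, fewer subjects are lost, but a raised ALT or AST that itself goes on to cross the threshold is still missed. Given why the study ended and how little it costs to close the gap, it should be fixed.

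**What to change.** In SAP 6.1.1:

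- Add a by-arm count of each of the four criteria at any time after the first dose, with both periods combined.
- Report the off-treatment counts for all subjects with off-treatment data, split by normal or abnormal off-treatment baseline. Keep the normal-baseline row as the new-onset line, and state which tests define normal.
- Add one eDISH plot using peaks over the combined period.

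A 7-day laboratory tail matching the adverse event window in SAP 6.1 is optional.

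The cost is a few table rows and one plot, with no new data collection. The reported liver counts may rise.
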